#### 49 **Group 1: Standard of care group:**

Dyads randomized to the control group will be discharged per local hospital policy with instructions from their team. They will be given the contact number of the study team to call as needed and will then be seen at day 30 of an in-person visit. We will follow the medical record of the patients to evaluate for intervening readmissions but will not call them specifically. The standard of care of these patients is usually either follow-up as needed or occasional phone calls as needed by the clinical team. The standard of care also depends on the acuity of the presentation and the ability of the patient to follow-up. For this study, we will require a 30-day visit from the patient and caregiver.

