#### 54 **Group 2: Health-IT only group:**

Training at the time of discharge: The Patient Buddy app with preloaded caregiver and patient interfaces will be shown to the subjects and caregivers with detailed instructions including: User Guide of Patient Buddy, Quick Reference Sheets for Case Coordinator to give the Patient and Caregiver with screenshots and tips and tricks for maneuvering around the modules, Powerpoint presentation that goes through the workflows for patients and caregivers, and one on one training for the Case Coordinator given by the CITI Representative. In addition, administration of five orientation questions (what is the date, what is the time, what is the year, who am I and where are you?) and EncephalApp Stroop will be taught to the caregiver. The call-in numbers for the nurse coordinator, GI physician on call and the contact information for the

1 principal investigator will also be programmed into the app. A detailed training session will be performed over the next hour by the coordinator  
 2 and the PI to both the patient and the caregiver. This training will be tailored to the specific issues faced by the patient while they were  
 3 hospitalized. The individualized login and passwords for each patient and their caregiver will be established and given to them. A copy will be  
 4 kept with the nurse coordinator in case the subjects forget their codes. These will be reset upon return of the devices at the end of the study.  
 5 The connectivity and messaging system in-built into the Patient Buddy App will then be checked and the control center of the CITI  
 6 communications notified of this enrollment. This will also be checked by sending messages by the patient and caregiver through the App to  
 7 the coordinator and the PI (Figure 3 demonstrates the data flow). In the health-IT only group, there will be daily contacts between patients,  
 8 caregivers and the clinical teams via the App. The only visit scheduled for the study will be at day 30 when the study will be completed.  
 9 However, if there are issues that come up during the intervening period detected via the App, the clinical team will reach out and determine  
 10 with the patients and caregivers if an ad hoc intervening visit is required. The team will not meet with patients or caregivers if they are scheduled  
 11 to be seen as standard of care in their clinics in between the 30 days unless specifically required by the symptoms or if the patient requires  

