 12 readmission. If the patient requires readmission before day 30, their participation will end at that time.

13 **Group 3: Health-IT+Scheduled Follow-up Group:**

14 This group will undergo the training at discharge similar to what was performed in group 2 but we will also intersperse the 30 day follow up with  
 15 one visit and 2 scheduled phone calls as below. Visit Scheduled: Patients and caregivers will be formally called at day 7 and 21 post discharge  
 16 by the study team to inquire about issues that were not communicated via PatientBuddy. We will also perform a study visit at day 15 and day  
 17 30 with both patients and caregivers to define any new changes in the patient's condition, elicit feedback throughout the process and at the day  
 18 visit, returning the devices and resetting them. No additional charges will be generated from the study during these visits.

19 The week 2 visit will include vital signs as well as the discussion of any issues with the buddy app, patient medication update, and any new  
 20 medical issues. The subject will also be given the EncephalApp stroop and orientation test for the week like in group 2. Study staff may also  
 21 observe the caregiver and subject perform their daily app entries. (subject may document medications taken, abdominal girth measurement,  
 22 and daily weight. The caregiver may document medications, daily weight, abdominal girth, orientation questions and stroop test) The study  
 23 staff will offer guidance as needed to complete these tasks. If the patient has a >10lb weight gain from baseline, a >5 inch girth increase, and/  
 24 or is febrile, the study team will notify the hepatologist on service and the PI for direction. No blood will be collected for the study and/or tests  
 25 run for study purposes at any time. However, if the subject is febrile, has overt encephalopathy, is bleeding, and/or is more decompensated,  
 26 the study team will alert the medical team and coordinate care as needed. Any care performed as a result of the findings from this visit will be  
 27 conducted per standard of care by the medical team."

28 FOR GROUPS 2 AND 3: If the subject is re-admitted, they meet the endpoint and their participation will  
 29 end. We will contact the caregiver and coordinate a return of the smartphones and end of study elements. We will also  
 30 request a discharge summary from the outside hospital if they were hospitalized outside of McGuire VAMC. If the patient  

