56 meet with the patient and his/her caregiver at this day 30 visit and will not generate any costs for the pt. We will collect the smartphones and  
57 have the patient and caregiver complete a survey regarding their experience with the app. The pt and caregiver will be together. The questions  
58 to be asked are uploaded to this submission."

59 Decision regarding avoidable readmissions: This will be made by analyzing the discharge summary of the hospitalized patients and will be  
60 classified into avoidable or unavoidable by the committee with three hepatologists (1 each from the 3 sites). The decision regarding avoidability  
is based on the question whether could a clinic visit or earlier communication/education with patient and caregiver prevented this admission.

1 There is no specific hard and fast rule about which admissions are classified as one or the other, which is why a committee is necessary. On  
2 the whole, admissions for elective paracentesis, thoracentesis, early stages of hepatic encephalopathy etc are usually avoidable but those  
3 related to infections, severe hepatic encephalopathy, variceal bleeding etc are usually not considered avoidable. However, since each case is  
4 unique, all discharge summaries of patients admitted within 30 days will be sent to the committee to review and vote. The committee will not be  
told about the assignment of the patients.

5 SAEs: we do not anticipate SAEs i.e. re-admissions to be related to the App itself because that is what is the focus of the study. Therefore,  
6 SAEs simply associated with admissions will not be reported to the IRB. We do not expect other SAEs directly related to the App to appear in  
7 this study.

8  
9  
10  
11  
12  
13  
14 **Active Data Collection**

15  
16. \* **Describe the technology chosen for collecting the data and transmitting data securely over the internet. Give the rationale  
for selecting this technology:**

17 For groups 2 and 3, we will use the Patient buddy app. This has been described in great detail in the uploaded grant but the details are below.  
18 **Patient Privacy and Security:** The App is HIPAA compliant with federal regulations regarding Privacy and Security. Patient Buddy is  
19 considered a Business Associate under the terms of the final HIPAA Omnibus rule. The data management of this study will operate using a  

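### The avoidability question overlaps with the contact that health-IT adds, and nothing keeps that contact out of the adjudicated summaries, so like admissions could be labelled differently by arm

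*Combined protocol and SAP*

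**What the plan says.** The paragraph on the decision regarding avoidable readmissions (item 4, the proposed research) says that avoidability "is based on the question whether could a clinic visit or earlier communication/education with patient and caregiver prevented this admission". It adds: "There is no specific hard and fast rule about which admissions are classified as one or the other". It then gives examples by type. In its words, "admissions for elective paracentesis, thoracentesis, early stages of hepatic encephalopathy etc are usually avoidable but those" for infections, severe encephalopathy or variceal bleeding usually are not. Because each case is "unique, all discharge summaries of patients admitted within 30 days will be sent to the committee to review and vote". Three hepatologists, one per site, decide. They are not to be "told about the assignment of the patients", and Specific Aim 1 calls the committee blinded.

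The arms differ in contact after discharge:

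- **Group 1:** the study team follows the records of the "patients to evaluate for intervening readmissions but will not call them specifically".
- **Group 2:** "In the health-IT only group, there will be daily contacts between patients", caregivers and the clinical teams, with ad hoc visits if the app shows a problem.
- **Group 3:** the same, plus calls at days 7 and 21 and an interim visit ("We will also perform a study visit at day 15 and day" 30).

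Avoidable readmission is the Aim 1 outcome and the basis of the sample size. Amendment 2 later merges the two health-IT groups and sets 1:1 randomisation with 232 patients.

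**The concern.** The question is counterfactual: would a visit or earlier communication have prevented this admission? Whether such contact had already taken place is a natural input to the answer. Suppose two patients are readmitted with the same recurrent ascites on day 20. If one record shows no contact since discharge, an adjudicator can easily say that earlier contact might have helped. If the other shows daily messages and a recent visit, the same adjudicator may say that contact was tried and failed. Treatment could then change the label as well as the event, and the avoidable rate could fall in health-IT with no fewer readmissions. Withholding the arm name does not by itself hide a contact history.

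**Working it through.** **1. Where contact could reach the adjudicators.**

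- The source is the discharge summary, and no redaction step is described.
- App and call findings feed into care. The section on provisions for adverse events has the coordinator contact the medical team, relay and document instructions, and arrange clinic appointments. A readmission history could record these.
- The committee has one hepatologist per site. The section on communication between sites has a hepatologist investigator from each site discuss, on quarterly calls, whether readmissions could have been prevented. The randomisation paragraph sends the sequence to the sites beforehand.

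None of this shows that contacts are seen. It shows that nothing in the plan prevents it.

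**2. The plan's own figure.** Inputs from the sample size justification: 20% v 9% avoidable, 80% power, alpha 0.05, 135 per arm. A three-group chi-square with rates 20%, 9% and 9% has mean rate 0.38/3 = 0.1267. Its noncentrality is 135 × (0.0733² + 2 × 0.0367²)/(0.1267 × 0.8733) = 9.84 on 2 degrees of freedom. Power is 80.9%, so the figure reproduces. Dropout: 405/0.90 = 450, also as stated.

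**3. Effect of unequal labelling when the app does nothing.** Assumptions:

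- the true avoidable rate is p1 = 0.20 in both arms;
- a share s of avoidable labels is lost in health-IT only, so the observed rate there is p2 = 0.20(1 − s);
- n = 116 per arm (232/2; an even split is assumed, since the amendment does not give the actual one);
- the test is a two-sided two-proportion z test at 0.05 (the documents name no test).

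With p̄ = (p1 + p2)/2, SE0 = √[2p̄(1 − p̄)/n] and SE1 = √{[p1(1 − p1) + p2(1 − p2)]/n}, the chance of significance favouring health-IT is Φ[(p1 − p2 − 1.96·SE0)/SE1].

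For s = 20%: p2 = 0.16, p̄ = 0.18, SE0 = 0.0504, SE1 = 0.0504. Then (0.04 − 0.0989)/0.0504 = −1.17, and Φ = 12.1%.

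| Labels lost in health-IT (assumed) | Observed rates | Chance of significance for health-IT |
|---|---|---|
| 0% | 20% v 20% | 2.5% |
| 10% | 20% v 18% | 5.8% |
| 20% | 20% v 16% | 12.1% |
| 25% | 20% v 15% | 16.9% |
| 30% | 20% v 14% | 22.8% |

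**4. Sensitivity to the base rate.** The sample size text can also be read as 20% of the 33% who are readmitted: 0.20 × 0.33 = 6.6%. At 116 per arm the chance is then 6.2% with 20% lost (6.6% v 5.28%) and 9.6% with 30% lost (6.6% v 4.62%).

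**5. Can all-cause readmission replace the endpoint?** It needs no avoidability label. But the same 11-point difference, 33% v 22%, needs 258 per arm, and power at 116 per arm is 46.6%. It can serve as a check at this size, not as a substitute.

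**The case against.** A reader might infer that the criterion is the randomised treatment itself, that even a blinded panel must label the arms differently, and that the bias must favour the app. The documents do not support that.

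- The committee is blinded. No passage says that app messages or study calls appear in readmission summaries: app data go to the vendor's server, and some summaries come from outside hospitals.
- The examples by type of admission do not depend on arm, and they already resemble the rule one would want.
- Education is given to all arms, some standard-of-care patients have a 2-week visit, and Group 2 has no scheduled study visit before day 30. A visit can therefore be untried in health-IT, and contact can have occurred in control.
- Direction is open. A summary showing an app alert that was not acted on could make a health-IT admission easier to call avoidable.
- The shares of labels lost have no source in the documents.

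All of this stands, and it limits what can be said about size and sign. It does not show that labels are comparable across arms. The examples apply only usually, the plan disclaims any fixed rule, and the counterfactual question remains the operative criterion. Specific Aim 1 promises a detailed analysis of 30-day readmissions, but no comparison of all readmissions by arm is specified as a check.

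**Conclusion.** The concern holds as a risk, not as a demonstrated bias. The Aim 1 endpoint is defined partly by the kind of contact that is randomised, and its protection rests on withholding the assignment. Unequal labelling requires contacts to be visible in the summaries or known to the site hepatologists, which the documents leave open. If it occurs, it probably favours health-IT.

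Within the assumed range of 10% to 30% of labels lost, the chance of a false finding for the app goes from 2.5% to between 5.8% and 22.8% on the 20% base rate. It is smaller on the 6.6% reading. These figures rest on an even 116/116 split and on assumed shares. This should be fixed because prevention is cheap; it does not by itself invalidate the design.

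**What to change.** 1. **Instruction to the committee.** Judge avoidability from the diagnosis, precipitant and clinical state at presentation, building on the examples by type already in the plan. State that contact received after discharge is not to be weighed.
2. **Masking.** Before the vote, remove references to the app, study calls and interim visits from the summaries.
3. **Reporting.** Beside the avoidable-readmission result, show all 30-day readmissions by arm and the share judged avoidable in each. On the 20% reading with 20% of labels lost and no true effect, the total stays at 33% in both arms while the avoidable share falls from 20/33 = 61% to 16/33 = 48%. If the app truly prevented those 4 points, the total would fall to 29%. The two rows together help to tell the cases apart, within the limits of the power shown above.

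The cost is minor redaction work, one table, and slightly less comparability with the pilot's avoidability judgments. If readmissions have already been adjudicated, masked summaries can be voted on again.

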**secured from improper use and disclosure:**

1  
2 We will keep all data private by only using study IDs on the patient's paper charts and also storing all information on a secure, password-  
3 protected drive. The charts will be kept under lock and key in the offices of [name] and [name] and [name] which are only accessible to  
4 the study team. The password protected drives will only be accessible to the study team.

5  
6 **Patient Privacy and Security:** Patient Buddy™ is HIPAA compliant with federal regulations regarding HIPAA Privacy and Security. Patient  
7 Buddy is considered a Business Associate under the terms of the final HIPAA Omnibus rule. The data management of this study will operate  
8 using a secure hosted environment with a HIPAA compliant server and data storage network. Given the sensitivity and need for security in  
9 managing and handling personal health information (PHI), Patient Buddy has developed its application such that no data is stored on either  
10 any of the distributed devices. Only after verification and authentication of login credentials is established with the server, is any data pushed  
11 out to the appropriate devices. All data is transmitted to the server where it is controlled behind the network firewall.

12  
13 **Patient Buddy (App) Design and Implementation to Protect PHI:** The Patient Buddy App will be hosted at a secure data center using a  
14 HIPAA compliant server. The data center provides several key security features that contribute to the safeguarding of PHI. These data safety  
15 and security features include physical security of the data center and infrastructure; perimeter security of IP reputation; network security for  
16 intrusion detection, firewall and vulnerability; server security for OS, anti-virus and log management; along with procedures and protocols for  
17 data backups, security audits, access control, change controls, and the maintenance of policies and procedures. From an application and  
18 program management standpoint, Patient Buddy offers further security safeguards to protect PHI to include secure data deletion upon  
19 termination of services; administrative security that provides for secure access and two-factor authentication; program access control; security  
20 policies and procedures, incidence response protocols, and risk assessments monitored and updated by our privacy and security officer, as  
21 well as data management and application management processes. All Integration of exports from the EncephalApp Stroop will be handled  
22 with the same security and privacy concerns. At no time will any PHI be disclosed and all data will be filtered through the HIPAA compliant  
23 servers.

24 We will provide feedback on app usability with CITI quarterly by sending them a de-identified spreadsheet with survey results.

**25 \* Who will have access to study data:**

26 Only the study team will have access to the data only

**27 \* If the study will code (i.e. de-identify) the research data by replacing subjects' names with assigned subject IDs, explain the  
28 following aspects of the coding process:**

29 The codes will be assigned with subject sequential number, date of enrollment and whether this is a patient or a caregiver. The key will be  
30 kept on a secured hard drive accessible only to the study staff and will be destroyed after the minimum data retention period is over

31 **Non-VA Site Details\*** How will communication occur between sites for discussion of study conduct, unexpected problems, project  
32 modifications, and interim results:

33 A hepatologist study investigator will be selected to represent each of the three study sites. A conference call will be held quarterly and the 3  
34 site selected investigators will review and discuss the de-identified data to determine if any re-admissions could have been prevented. As  
35 questions and issues occur, the same group will be the conduit to problem solve as a group and keep the study team informed.

## 36 Study Population

37  
38. \* Provide the total number of individuals at VAMC: 300

39  
40. If this is a multi-Center Project, what is the total anticipated number of subjects across all sites: 900

**41. \* Provide justification for the sample size:**

42 Sample size: Prior studies and our cohort have shown a 30-day readmission rate around 33% using current practice, and of which 20% were  
43 considered avoidable. Per our preliminary data, the rate of 30-day avoidable readmission reduced to 5%. However, we will be circumspect  
44 and increase this relative avoidable readmission rate to 9%. In order to determine a similar reduction at 80% power at an  $\alpha = 0.05$  level of  
45 significance we would require 45 patients in the Health-IT+scheduled visits, 45 patients in the Health- IT only and 45 patients in the standard  
46 of care group per site leading to a total of 135 patients per site or 405 total patients. This will also include 405 caregivers. Allowing for a 10%  
47 dropout rate, we plan to we will enroll a total of 450 patients, of which 150 will be randomized to health-IT+scheduled visits, 150 to health-IT  
48 only and 150 to standard of care across all three sites. This will be accompanied by an equal number of the respective caregivers bringing the  
49 grand total of subjects across all three sites to 900.

50 Therefore at McGuire VAMC we will enroll 50 patients and 50 caregivers in each group for a total of 300 subjects (150 patients and  
50 caregivers).

51

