36 readmissions in patients with cirrhosis and their caregivers compared to standard of care.**

37  
38 As part of this specific aim, we will include 450 total cirrhotic patients and 450 caregivers (150 patients and 150 caregivers per center), who will  
39 be followed for 30 days post-discharge. The groups will be randomized 1:1:1 into a standard  
40 of care group, a group receiving health IT interventions who will receive PatientBuddy and EncephalApp Stroop with as-needed follow-up and  
41 another group that receives the same health IT interventions along with scheduled outpatient visits and calls within 30 days of discharge.  
42 Avoidable readmissions will be adjudged using a blinded adjudication committee and the differences between the three groups will be compared.  
43

44 The Health IT groups will be given iPhones loaded with the Patient Buddy app with caregiver and patient interfaces. They will be instructed  
45 extensively regarding the use of the App, which is preloaded with variables that associated with readmissions such as medications and  
46 adherence, issues with cognition and orientation and new symptoms. The patient and the caregiver will have separate devices linked to a device  
47 with the nurse coordinator through which daily communication will occur between patient/caregivers and the study team regarding previously  
48 identified risk factors associated with readmission. With this enhanced communication and educational value of the App, the study team will  
49 have greater access to events at patients' homes and the potential to prevent readmissions by intervening at that stage. The team will also  
50 engage the end-users (patients, caregivers and the nurse coordinator) by inquiring about their input in order to enhance the interface, user-  
51 friendliness and impact of the App. A detailed analysis of 30-day readmissions, including potential preventability with Patient Buddy will be  
52 performed. CITI will be responsible for establishing and monitoring the communication channels and implementation of the interfaces.  
53  
54  
55  
56  
57  
58  
59  
60

1 **Specific aim 2: To incorporate the opinion of key stakeholders (patients, caregivers and nurse coordinators) towards improving the**  
2 **Patient Buddy App in the prevention of readmission in cirrhosis**

3 The input of patients, caregivers and nurse coordinator and analysis of potential preventability of readmissions in specific aim 1 will be used  

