12 Justification: To increase generalizability  
13

14 **Protocol Amendment 2**  
15

16 Due to COVID-19 related gap in enrollment, funding shortfalls, and low likelihood of us reaching the  
17 original study goals, a re-evaluation of the data was done to see if we could combine the two health-IT  
18 groups. Avoidable readmissions were similar across the 2 health IT groups and therefore, instead of 1:1:1  
19 randomization, this was changed to 1:1 randomization with a total of 464 subjects ( 232 patients and 232  
20 caregivers).  
21

22 Justification: reduced enrolment requiring combination of the groups.  
23

24  
25  
26  
27  
28  
29  
30  
31  
32  
33  
34  
35  
36  
37  
38  
39  
40  
41  
42  
43  
44  
45  
46  
47  
48  
49  
50  
51  
52  
53  
54  
55  
56  
57  
58  
59

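### As worded, the control avoidable-readmission rate is 6.6% of patients (20% of 33%), and 135 per arm does not give the stated 80% power at that rate

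*Combined protocol and SAP*

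**What the plan says.** The sample-size item under Study Population (Combined protocol and SAP) starts from a "30-day readmission rate around 33% using current practice, and of which 20% were" judged avoidable. For the preliminary data it reports that "the rate of 30-day avoidable readmission reduced to 5" percent. To be cautious, the authors then raise the planning value: "and increase this relative avoidable readmission rate to 9%. In order to determine a similar reduction at 80% power at an" alpha of 0.05.

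The requirement is 45 patients per group per site, "of care group per site leading to a total of 135 patients per site or 405 total patients", which is 135 per arm over three sites. After an allowance for 10% dropout the target is 450 patients, 150 per arm.

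The item does not say whether 20%, 5% and 9% are shares of patients or of readmissions. It names no test and no sidedness. Specific Aim 1 adds only this: "Avoidable readmissions will be adjudged using a blinded adjudication committee and the differences between the three groups will be compared".

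Protocol Amendment 2 later merges the two health-IT groups: "this was changed to 1:1 randomization with a total of 464 subjects ( 232 patients and 232" caregivers. It gives no event rates and no power.

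**The concern.** In the sentence as written, *of which* points back to the readmissions. The avoidable rate under current practice is therefore one fifth of 33%, or 6.6% of discharged patients. The 9% is called *relative*, which leaves open that it too is a share of readmissions. The N, however, looks as if it was computed from much larger per-patient rates.

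The difference matters. A control arm of 135 would be expected to yield 135 × 0.066 = 8.9 avoidable readmissions on the literal reading and 135 × 0.20 = 27.0 if 20% is a share of patients. A null result means something quite different in the two cases. Without the denominator and the test, a reader cannot tell which trial was planned.

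**Working it through.** **Inputs** (sample-size item unless noted): readmission 33%; avoidable 20%, denominator in question; intervention 5% (preliminary) and 9% (planning); alpha 0.05; power 80%; 45 per group per site at three sites; dropout 10%. The 1:1:1 allocation is in Specific Aim 1; 232 patients at 1:1 is in Amendment 2. Assumptions: pairwise tests are two-sided, and both health-IT arms share one rate.

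**Formulas**
- Pairwise: power = Φ[(|p₁−p₂| − 1.96·s₀)/s₁], with s₀ = √[p̄(1−p̄)(1/n₁+1/n₂)] and s₁ = √[p₁(1−p₁)/n₁ + p₂(1−p₂)/n₂].
- Three-group: 2-df noncentral chi-square with λ = n·Σ(pᵢ−p̄)²/[p̄(1−p̄)] and critical value 5.991.

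**Step 1. The plan's own figure.** Take 20%, 9% and 9% of all patients.
- Three-group: p̄ = 0.1267. At n = 135, λ = 135 × 0.008067/0.11062 = 9.84 and power is 80.9%. Power is 79.96% at 132 and 80.28% at 133, so 133 per arm are needed.
- 133/3 sites = 44.3, rounded up to 45 per group per site. Then 45 × 3 = 135 per arm, 135 × 3 = 405, and 405/0.9 = 450. Every printed number is accounted for.
- Pairwise, same rates at 135: p̄ = 0.145, s₀ = 0.04286, s₁ = 0.04233. (0.11 − 0.0840)/0.04233 = 0.614, so power is 73%. For 80%, 160 per arm are needed.

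**Step 2. The sentence as written.** Control rate = 0.33 × 0.20 = 0.066. The intervention rate depends on what 9% or 5% is a share of:
- Share of readmissions, all-cause readmission held at 33%: 0.33 × 0.09 = 2.97%; 0.33 × 0.05 = 1.65%.
- Share of readmissions, unavoidable readmissions held at 0.33 − 0.066 = 26.4% of patients: 0.09 × 0.264/0.91 = 2.61%.
- Share of all patients: 9% or 5%.

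Worked case, 6.6% vs 2.97% at 135 per arm: s₀ = 0.02598 and s₁ = 0.02589. (0.0363 − 0.0509)/0.02589 = −0.565, so power is 28.6%. Three-group: λ = 2.96, power 31.8%.

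| Contrast at 135 per arm | Pairwise | Three-group |
|---|---|---|
| 6.6% vs 2.97% | 29% | 32% |
| 6.6% vs 2.61% | 35% | 40% |
| 6.6% vs 1.65% | 53% | 65% |
| 6.6% vs 5% | 8% | 8.5% |
| 6.6% vs 9% | an increase | an increase |

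For 6.6% vs 2.97%, 80% power would need 542 per arm pairwise or 440 three-group. Pooling both health-IT arms (135 vs 270) gives 42% for 2.97% and 71% for 1.65%.

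**Step 3. Amendment 2.** The final split is not given, nor whether 232 is before or after dropout. With 10% dropout, 232 × 0.9 = 208.8. The unequal splits are what would result if everyone had been randomized 1:1:1 and the health-IT groups then merged. Two-sided power:

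| Control : health-IT | 20% vs 9% | 6.6% vs 2.97% |
|---|---|---|
| 104:104 (10% dropout) | 62% | 23% |
| 70:139 (10% dropout) | 61% | 26% |
| 116:116 (no dropout) | 66% | 25% |
| 77:155 (no dropout) | 65% | 28% |

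A simulation check (400,000 runs, uncorrected chi-square) agreed with the formulas to about two percentage points. For the three-group test at 135 per arm it gave 78.8% for 20% vs 9% and 30.6% for 6.6% vs 2.97%.

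**The case against.** The best defence is that 20% and 9% were always per-patient rates and the phrasing is loose. The paragraph plans a reduction, and the preliminary 5% reads naturally as a rate among patients. If 9% is also per patient, a 6.6% control rate leaves nothing to reduce. Step 1 recovers every printed number on this reading, including why N is given per site. This stands as the most plausible explanation. It remains an inference, because no test is named, and it concedes that the rate sentence is wrong.

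It also does not settle the power for comparing health IT with standard of care, which is what the central hypothesis describes. With 20% vs 9%, one health-IT arm against control has 73% power two-sided. A one-sided test would give 82.5%, and pooling both health-IT arms would give 86%, but the item describes neither.

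Three stronger readings are tempting and are not supported:
- *That 135 per arm is an arithmetic error, or that the trial was planned with about 30% power.* The N is reproducible on the per-patient reading.
- *That N came from 33% vs 9%, an all-cause rate set against an avoidable one.* A two-sided pairwise calculation does give 45 per arm (79.99% at 44, 80.9% at 45). But that is 45 per arm in total, whereas the plan has 45 per arm per site, and nothing in the text proposes that contrast.
- *That the design in Amendment 2 is underpowered whatever the rates.* The shortfall holds for the 9% planning value. For 20% vs 5%, power is 89% to 94% over the same splits.

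**Conclusion.** The point holds in limited form. The rate sentence and the 80% claim cannot both be right as written. At the literal control rate of 6.6%, no two-sided pairwise, three-group or pooled calculation in the working reaches 80% with 135 per arm. With the 9% planning value as a share of readmissions, power is about 29% to 40%. The lower end assumes all-cause readmission stays at 33% in the health-IT arms, and the upper end assumes unavoidable readmissions stay at 26.4% of patients. The documents state neither.

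Most probably the wording is at fault and the N is not. On that view 135 per arm gives 80.9% for the three-group test and 73% for each pairwise comparison.

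The absence of a power statement in Amendment 2 is a secondary point and an omission, not a misstatement. For the 9% planning value its two-sided power is about 61% to 66% (20% vs 9%) or 23% to 28% (6.6% vs 2.97%).

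**What to change.** In the sample-size item:
- State the control and intervention avoidable-readmission rates as proportions of all discharged patients. If 20% is per patient, correct *of which*.
- Name the test and its sidedness, and say whether it is a three-group, pairwise or pooled comparison.
- Restate the power that 135 per arm gives for that test. For 20% vs 9% of patients this is 80.9% three-group and 73% pairwise two-sided. If the rates are shares of readmissions it is about 29% to 40%, and the assumption about all-cause readmission in the health-IT arms should be written down.

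Under Amendment 2, add one sentence giving the power for the actual split and saying whether 232 is before or after dropout.

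The cost is one reworded paragraph and one added sentence. No extra enrolment and no change to conduct are asked for. The downside is a less favourable stated power.
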